12.6.3 Exploratory Analysis

12.6.3.1 Questionnaires

12.6.3.1.1 FTND Questionnaire

The FTND questionnaire will be administered at Screening and the Day 90 Visit.

FTND score value and the number and percentage of subjects in each category (mild/moderate/severe) will be presented at Screening and Day 90 Visit. The percent change from Baseline in the FTND score at Day 90 will also be presented. The changes in the categories will also be presented in a shift table.

All summaries and shift tables will be performed on the PP, FAS and Compliant populations.

The data will be presented in the below outputs:

TFL number	Title
TABLES	
15.2.1.4.1	Summary of Demographics and Other Baseline Characteristics – Safety Population
15.2.1.4.2	Summary of Demographics and Other Baseline Characteristics – FAS
15.2.1.4.3	Summary of Demographics and Other Baseline Characteristics – PP Set
15.2.1.4.3.1	Summary of Demographics and Other Baseline Characteristics by Sex – PP Set
15.2.1.4.3.2	Summary of Demographics and Other Baseline Characteristics by Cigarette Consumption – PP Set
15.2.4.34.1	Summary of Fagerström Test for Nicotine Dependence Results – PP Set
15.2.4.34.2	Summary of Fagerström Test for Nicotine Dependence Results – FAS

TFL number	Title
15.2.4.34.3	Summary of Fagerström Test for Nicotine Dependence Results – Compliant Population
LISTINGS	
15.3.6.11	Listing of Fagerström Test for Nicotine Dependence Results

12.6.3.1.2 Urge-to-Smoke Questionnaire of Smoking Urges Brief

The QSU-brief will be administered daily from Days -1 to 5, and Days 30, 60 and 90. The change from baseline will be calculated for the total score and the two domain scores (relief and reward). The total score and two domain scores, along with the percent change from baseline will be summarized. The answers to the individual questions, along with the domain scores, total scores, changes and percent changes from baseline will be listed.

The profiles of the raw means from baseline to Day 90 Visit for the total score and two domain scores will be produced.

The analysis will be performed separately for each post-baseline timepoint in the domain and total scores. An ANCOVA model will be used with terms for baseline QSU-BRIEF score, sex, average daily mCC consumption over the last 4 weeks as reported during screening, and randomization arm. No adjustment will be made for multiple comparisons. The SAS code to be used is similar to the model reported in Section 12.6.1.3 "Sensitivity Analysis", amended as appropriate to obtain the required comparisons.

LS means for each randomization arm along with the difference (THS 2.2 Menthol - mCC) and (THS 2.2 Menthol – SA) with 95% CI will be presented in the tables.

All figures, summaries and analyses will be performed on the PP Set and the FAS.

The data will be presented in the below outputs:

TFL number	Title
FIGURES	
15.1.2.12.1	QSU-brief Total Scores and Percent Change Mean and 95% CI – PP Set
15.1.2.12.2	QSU-brief Total Scores and Percent Change Mean and 95% CI – FAS
15.1.2.13.1	QSU-brief Total Scores Least Squares Means Differences and 95% CI – PP Set
15.1.2.13.2	QSU-brief Total Scores Least Squares Means Differences and 95% CI – FAS
TABLES	
15.2.4.35.1	Descriptive Statistics of QSU-brief Factors and Total Scores – PP Set
15.2.4.35.2	Descriptive Statistics of QSU-brief Factors and Total Scores – FAS
15.2.4.36.1	Analysis of QSU-brief Factors and Total Scores – PP Set
15.2.4.36.2	Analysis of QSU-brief Factors and Total Scores – FAS

TFL number	Title
LISTINGS	
15.3.6.12	Listing of QSU-brief Questionnaire Results

12.6.3.1.3 Modified Cigarette Evaluation Questionnaire

The mCEQ will be administered daily from Days -1 to 5, and Days 30 Visit, 60 Visit and 90 Visit. All summaries, profiles and analysis will be presented for the THS 2.2 Menthol and mCC only. The mCEQ is not captured for the SA arm.

The domain scores, along with the percent change from baseline will be summarized. The answers to the individual questions, along with the domain scores, changes and percent changes from Baseline will be listed.

The profiles of the raw means from baseline to Day 90 for the five subscale scores will be produced.

The analysis will be performed separately for each post-baseline timepoint in the subscales. An ANCOVA model will be used with terms for baseline mCEQ score, sex, and average daily mCC consumption over the last 4 weeks as reported during screening. No adjustment will be made for multiple comparisons.

The SAS code to be used is similar to the model reported in Section 12.6.1.3 "Sensitivity Analysis".

LS means for each product along with the difference (THS 2.2 Menthol - mCC) with 95% CI will be presented in the tables.

All figures, summaries and analyses will be performed on the PP Set and the FAS.

The data will be presented in the below outputs:

TFL number	Title
FIGURES	
15.1.2.14.1	MCEQ Subscales Mean and 95% CI of Percent Change from Baseline – PP Set
15.1.2.14.2	MCEQ Subscales Mean and 95% CI of Percent Change from Baseline – FAS
15.1.2.15.1	MCEQ Subscales Least Squares Means Differences and 95% CI – PP Set
15.1.2.15.2	MCEQ Subscales Least Squares Means Differences and 95% CI – FAS
TABLES	
15.2.4.37.1	Descriptive Statistics of MCEQ Subscales – PP Set
15.2.4.37.2	Descriptive Statistics of MCEQ Subscales – FAS
15.2.4.38.1	Analysis of MCEQ Subscales – PP Set
15.2.4.38.2	Analysis of MCEQ Subscales – FAS

TFL number	Title
LISTINGS	
15.3.6.14	Listing of MCEQ Questionnaire Results and Changes from Baseline

12.6.3.1.4 Minnesota Nicotine Withdrawal Questionnaire

The MNWS will be administered daily from Days 0 to 6, and Days 31, 61 and 91 for the assessment of Day-1 to Day 5, and Days 30, 60 and 90 as it is a 24-hour recall questionnaire.

All summaries, profiles and analysis will be presented for the day before the assessment in the THS 2.2 Menthol, mCC and SA arms.

The total score, along with the percent change from baseline will be summarized. The answers to the individual questions, along with the total score, the changes and percent changes from baseline will be listed.

The profiles of the raw means from baseline to Day 90 for the total score will be plotted.

The analysis will compare each post baseline timepoint separately for the total score. An ANCOVA model will be used with terms for baseline score, sex, and average daily mCC consumption over the last 4 weeks as reported during screening. No adjustment will be made for multiple comparisons.

The SAS code to be used is similar to the model reported in Section 12.6.1.3 "Sensitivity Analysis".

LS means for each product along with the difference (THS 2.2 Menthol - mCC) and (THS 2.2 Menthol – SA) with 95% CI will be presented in the tables.

All figures, summaries and analyses will be performed on the PP Set and the FAS only.

The data will be presented in the below outputs:

TFL number	Title
FIGURES	
15.1.2.16.1	MNWS Total Score Mean and 95% CI of Percent Change from Baseline – PP Set
15.1.2.16.2	MNWS Total Score Mean and 95% CI of Percent Change from Baseline – FAS
15.1.2.17.1	MNWS Total Score Arithmetic Least Squares Means and 95% CI – PP Set
15.1.2.17.2	MNWS Total Score Arithmetic Least Squares Means and 95% CI – FAS
TABLES	
15.2.4.39.1	Descriptive Statistics of MNWS Total Score – PP Set
15.2.4.39.2	Descriptive Statistics of MNWS Total Score – FAS

TFL number	Title
15.2.4.40.1	Analysis of MNWS Total Score – PP Set
15.2.4.40.2	Analysis of MNWS Total Score – FAS
LISTINGS	
15.3.6.13	Listing of MNWS Questionnaire Results

12.6.3.1.5 Human Smoking Topography Questionnaire

The HST questionnaire will be administered on Days 0, 4, 30, 60 and 90.

The number and percentage of subjects in each category of the items of the questionnaire will be summarized. The individual responses will be listed.

All summaries will be performed on the FAS.

The data will be presented in the below outputs:

TFL number	Title
TABLES	
15.2.4.41	Descriptive Statistics of HST Questionnaire Data – FAS
LISTINGS	
15.3.7.2	Listing of HST Questionnaire Results

12.6.3.2 Human Smoking Topography Parameters

The HST assessments will take place on Day 0, Day 1, Day 4, Day 30, Day 60 and Day 90 in the THS 2.2 Menthol and mCC arms only, if mCC are compatible with the HST SODIM® device. On Day 0, Day 1 and Day 4 the HST will be conducted on each product use. On Day 30, Day 60 and Day 90 the HST will be recorded over a 4-hour period only.

The per puff parameters are shown in Table 8 and the per cigarette parameters are shown in Table 9.

The per-cigarette parameters derived from the HST assessments will be averaged per day and summarized along with their changes from baseline. The per-puff and per-cigarette parameters will be listed. In addition the randomization arm mean and 95% CI per cigarette parameters will be presented graphically.

The averaged per-cigarette parameters will be analysed on Days 1, 4, 30, 60 and 90 separately using an ANCOVA model with terms for baseline score, sex, average daily mCC consumption over the last 4 weeks as reported during screening, and randomization arm. No adjustment will be made for multiple comparisons.

The SAS code will be the same as described in Section 12.6.1.3 "Sensitivity Analysis".

LS means for each product along with the difference (THS 2.2 Menthol - mCC) and 95% CI will be presented in the tables.

All figures, summaries and analyses will be performed on the FAS by product and product use categories.

The data will be presented in the below outputs:

TFL number	Title
FIGURES	
15.1.2.18	HST per Cigarette Parameters Mean and 95% CI of Percent Change from Baseline by product use category – FAS
TABLES	
15.2.4.42	Descriptive Statistics of HST Parameters per Cigarette – FAS
15.2.4.43	Analysis of HST Parameters per Cigarette – FAS
LISTINGS	
15.3.7.1	Listing of HST Assessments and Changes from Baseline

12.6.3.3 CYP2A6 Activity

CYP2A6 activity will be measured in plasma on Day 0, Day 6 and Day 91. In this study the CYP2A6 activity will be calculated using the metabolic ratio of trans 3' hydroxycotinine and cotinine, as described in Section 7.1.4 "CYP2A6". Descriptive statistics of the values and percent change on Days 6 and 91 from Baseline and supportive listings will be provided.

The analysis will compare the log-transformed Day 6 values between the THS 2.2 Menthol and mCC arms and between the THS 2.2 Menthol and SA arms.. ANCOVA models will be used with terms for log-transformed baseline, sex, average daily mCC consumption over the last 4 weeks as reported during screening and study arm. No adjustment will be made for multiple comparisons. If the results from the Day 6 analysis are significant (one-sided p-value ≤ 0.025) then the statistical significance will be repeated for the analysis at the Day 91 values. The SAS code will be similar to that described in Section 12.6.1.3 "Sensitivity Analysis".

Geometric LS means for each product along with the ratio (THS 2.2 Menthol : mCC) and 95% CI will be presented in the tables

CYP2A6 activity will also be examined to compare the reductions in THS 2.2 Menthol vs. SA using the same methodology as above.

If there are any CYP2A6 assessments performed within 5 half-lives since the use of a concomitant medication affecting CYP2A6 activity, the analysis will be repeated by excluding these assessments for both the PP Set and FAS

All summaries and analyses will be performed on the FAS and PP Set.

The data will be presented in the below outputs:

TFL number	Title
TABLES	
15.2.4.44.1	Descriptive Statistics of CYP2A6 Activity (%) – PP Set
15.2.4.44.2	Descriptive Statistics of CYP2A6 Activity (%) – FAS
15.2.4.45.1	Analysis of CYP2A6 Activity – PP Set
15.2.4.45.2	Analysis of CYP2A6 Activity – FAS
LISTINGS	
15.3.6.16	Listing of CYP2A6 Activity and Changes from Baseline

12.6.3.4 Relationship between BoExp and NEQ

The analysis of the relationship between NEQ and primary and secondary BoExp will be reported in a separate report as stated in Section 9 “CHANGES FROM THE PROTOCOL SPECIFIED STATISTICAL ANALYSIS”.

12.6.3.5 Relationship Between Risk Markers and NEQ

The analysis of the relationship between risk markers and NEQ will be reported in a separate report as stated in Section 9 “CHANGES FROM THE PROTOCOL SPECIFIED STATISTICAL ANALYSIS”.

12.6.3.6 Ames Mutagenicity Test

The 24 hour urine collection for the Ames mutagenicity test will be on Day 0, Day 5 and Day 90.

Descriptive statistics of the values and percent changes on Day 5 and Day 90 from Baseline of the YG1024+S9 mutagenicity will be provided, along with listings.

All summaries will be performed on the FAS, and PP Set.

The data will be presented in the below outputs:

TFL number	Title
TABLES	
15.2.4.46.1	Descriptive Statistics of Ames Mutagenicity Test (YG1024+S9) (units) – PP Set
15.2.4.46.2	Descriptive Statistics of Ames Mutagenicity Test (YG1024+S9) (units) – FAS
LISTINGS	
15.3.5.1	Listing of Mutagenicity Results

12.6.3.7 Visual Inspection of the Tobacco Plugs

The collection of the tobacco plugs from the THS 2.2 Menthol products will be performed on Days 1 to 5, and Days 30, 60 and 90. The number and percentage of tobacco plugs showing each of the following criteria will be summarized by day: “Ashes not anymore visible when shooting picture”; “No tobacco in plug”; “Not enough tobacco in the plug to perform the analysis”; “Tobacco plug destroyed, analysis impossible”; “No tobacco plug in the vial”; “Other error”.

All summaries will be performed on the FAS only.

The data will be presented in the below outputs:

TFL number	Title
TABLES	
15.2.4.47	Descriptive Statistics of Visual Inspection of the THS 2.2 Menthol Tobacco Plugs Data – FAS
LISTINGS	
15.3.6.17	Listing of Visual Inspection of the Tobacco Plugs

12.6.3.8 Filter Analysis

The filter analysis from the THS 2.2 products will be performed from Days 1 to 5. Descriptive statistics will be provided for smoke nicotine in filter and UV absorbance at 310 nm along with listings.

The data will be presented in the below outputs:

TFL number	Title
TABLES	
15.2.4.48	Descriptive Statistics of Filter Analysis from the THS 2.2 Menthol Products – FAS
LISTINGS	
15.3.6.18	Listing of Filter Analysis Data

12.6.3.9 Product preference analysis

The product preference as asked at admission will serve as a sensitivity analysis for the product exposure.

All summaries will be produced for the FAS.

These data will also be presented categorized separately by product preference and by product use categorization during periods 2-4 (see Section 6.3.3.1 “Dual-use”).

The data will be presented in the below outputs:

TFL number	Title
TABLES	
15.2.4.49	Summary of Average Daily Product Use in Ambulatory Period by Preferred Product Declared at Admission – FAS
15.2.4.50	Summary of Product Use Categories by Preferred Product Declared at Admission – FAS

12.6.4 Safety Evaluation

Safety variables monitored in this study include: AEs; vital signs (systolic and diastolic blood pressure, pulse rate, respiratory rate); spirometry; ECG data; concomitant medication, clinical chemistry, hematology, urine analysis safety panel, BMI, physical examination, respiratory symptoms (cough assessment).

12.6.4.1 Safety Reporting

The primary analysis of Safety parameters will be conducted on the Safety population as described in Section 12.1.3 “Descriptive statistics”. AE and laboratory findings summaries will be produced also for the Full Safety population.

12.6.4.2 Adverse Events

A product emergent AE is defined as an AE that occurs after first product use or that is present prior to first product use and becomes more severe after first product use. All other AEs will not be summarized but provided in listings only.

All AEs occurring from the signing of informed consent will be recorded electronically. However, only product emergent AEs will be summarized. The AE listings will include all AEs captured in the database at any time during the study (including those from subjects who were not in the safety population).

In general, AE summary tables reporting the number of events and the number and percentage of subjects reporting at least one AE will be produced by study arm for the Pre-Randomization and Randomized periods, as reported in Section 12.6.4.1 “Safety Reporting”. AE data during the Randomized period will also be presented stratified by Confinement, Ambulatory, and Safety Follow-up.

Ambulatory AE data will also be reported by product use category (see Table 20) defined on product use over the whole ambulatory period. In particular, the general product use categories for THS 2.2 will be used, and the [Predominantly Abstinence] and [Smoking Abstinence] categories will be presented for THS 2.2 Menthol and mCC arm if at least one subject is associated to these categories.

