12.1.2 Definitions for Statistical Data Analysis

Baseline:

In general, baseline will be the last available time-point prior to Day 1, 06:30 AM.

THS 2.2 Menthol users: Subjects switching from mCC to THS 2.2 Menthol whose product use pattern categorization is primarily THS 2.2 Menthol or predominantly THS 2.2 Menthol over a defined period will be considered as THS 2.2 Menthol users during that period.. See Section 12.3 for further details on the product use.

Dual use:

Subjects switching from mCC to THS 2.2 Menthol whose product use pattern categorization is dual mostly THS 2.2 Menthol, dual balanced or dual mostly CC over a defined period will be considered as dual users. See Section 12.3 for further details on the product use.

CC users:

Subjects switching from mCC to THS 2.2 Menthol or subjects continuing to use mCC whose product use pattern categorization is primarily CC or predominantly CC over a defined period will be considered as CC users during that period. See Section 12.3 for further details on the product use.

Smoking abstinence:

Data and information contained in this document are considered to constitute trade secrets and confidential commercial information, and the legal protections provided to such trade secrets and confidential information are hereby claimed under the provisions of applicable law. No part of this document may be publicly disclosed without the written consent of Philip Morris Products S.A.

Smoking abstinence during a defined period is defined as using no tobacco-containing product as reported by the subject on the electronic diary.

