12.3 Product use

The FDA Draft Guidance on Modified Risk Tobacco Product Applications Draft (Section VI-A-2) (FDA, 2012a), FDA requires that an MRTP Application should contain scientific evidence about the effect the product may have on tobacco use behavior among current tobacco users including consideration of areas such as the expected rates of use of the tobacco product by current tobacco users and the use of the tobacco product in conjunction with other tobacco products.

Although subjects being requested to use solely the product allocated to their respective study arm it is considered that during the ambulatory period not all subjects randomized to the THS2.2 Menthol arm might be exclusively using THS2.2 Menthol at all times during the study. Subjects may concomitantly use THS 2.2 Menthol and CC (dual-use). To assess dual use of THS 2.2 Menthol and CC, PMI has defined dual-use with regards to using THS 2.2 Menthol in the following way:

[figure not shown]
Dual-use will be calculated as percentage based on their reported THS 2.2 Menthol Tobacco Sticks consumption and the number of conventional cigarettes smoked (menthol and non-menthol) by study period:

- on Day 30, using the reported number of cigarettes and/or Menthol Tobacco Sticks consumption since time of Discharge,
- on Day 60, using the reported number of cigarettes and/or Menthol Tobacco Sticks consumption after Day 30 and
- on Day 90, using the reported number of cigarettes and/or Menthol Tobacco Sticks consumption after Day 60.

Data and information contained in this document are considered to constitute trade secrets and confidential commercial information, and the legal protections provided to such trade secrets and confidential information are hereby claimed under the provisions of applicable law. No part of this document may be publicly disclosed without the written consent of Philip Morris Products S.A.

Figure 2 presents a detailed overview on the definition of the product use categories:

Figure 2 - Product Use Pattern Categorization

The more granular categorization scheme will be used for the definition of the per-protocol population and for the description of the product use patterns observed in the study whereas the less granular scheme will be used for the presentation of other study endpoints (e.g. safety endpoints) to better understand the impact of product.

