12.4.3 Safety Population

The safety population consists of all the subjects who had at least one exposure to THS 2.2 Menthol (product test at Admission Day). Subjects in the safety population will be analyzed according to actual exposure. Although subjects that were enrolled at the site that was terminated due to ICH/GCP uncompliance will be excluded from the safety population, they will be summarized within the Full Safety Population (see Section 12.4.4).

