10.3 Safety Populations

10.3.1 Safety Population

Before randomization, the safety population consists of all the subjects who had at least one exposure to THS 2.2 Menthol (including the product test at Admission Day). This also includes any randomized subjects who had no valid safety assessment post-randomization.

After the randomization, the safety population includes all randomized subjects who had at least one valid safety assessment post-randomization. Subjects in the safety populations will be analyzed according to product use categories defined over the whole ambulatory period.

Although subjects that were enrolled at the site that was terminated due to ICH/GCP non-compliance will be excluded from the safety population, they will be summarized within the Full Safety Population (see section 10.3.2 “Full Safety Population”).

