12.1.1 Stratified Presentation

The following summaries will be produced by randomization arm, stratified by sex (male vs. female) and mCC consumption (10-19 mCC/day vs. >19 mCC/day) for the PP set at period 1 and 4:

- Demographics and Baseline Characteristics
- COHb, and MHBMA, 3-HPMA, S-PMA and total NNAL adjusted for creatinine.
- Product use

Summaries of data by product use categories will be produced for the product use time periods 1 to 4 (see Table 20), as appropriate.

Summaries of safety data will be provided stratified by pre-randomization and randomized period (see Table 20).

All endpoints will be summarized stratified by time point as appropriate.

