12.1.5 Handling of Dropouts or Missing Data (including outside the limits of quantification)

For laboratory parameters:

Values below the lower limit of quantification (LLOQ) will be imputed using LLOQ/2. For values above the upper limit of quantification (ULOQ), the ULOQ will be imputed.

The number of values below LLOQ or above ULOQ will be presented in each summary table. If 50% or more data are below LLOQ or above ULOQ, only the number (%) of value below LLOQ or above ULOQ will be reported in the summaries, together with minimum and maximum of the observed values.

Missing data at Baseline will not be imputed.

For BoExp:

- A last observation carried forward (LOCF) approach will be implemented to replace all missing data with the last available data for each parameter being assessed.
- For parameters assessed at several timepoints during a visit, the last available data at the timepoint being assessed collected at previous study visit will be used in the analyses. For example, if on Day 5, the evening assessment (20:00-23:00) is missing for COHb, the evening assessment from Day 4 will be used for analysis regardless whether other COHb assessments are available at Day 5.

For daily product use data in safety summaries:

- Product use categories will be defined based on percentage of THS 2.2 Menthol use calculated by averaging non missing consumption data over the entire ambulatory time interval.

For daily product use data in non-safety analyses and summaries:

- If at least 75% of the daily product use assessments over a period are available, with no more than 7-days of consecutive missing data:
 - Product use categories will be defined based on percentage of THS 2.2 use calculated by averaging non missing consumption data over the analysis interval.
 - Compliance to randomized product will be defined based on the available product use data.
- If less than 75% of the daily product use assessments over a period are available, or product use data is missing over a period of more than 7 consecutive days:
 - Product use categories will be defined based on percentage of THS 2.2 use calculated by considering the missing product use data as the CC use reported at Baseline.
 - Compliance to randomized product will be defined by considering the missing product use data as the CC use reported at Baseline.

For MNWS, QSU-brief, and MCEQ questionnaire data:

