15.2.6.4.2	Summary of Adverse Events by Product Use Category, System Organ Class and Preferred Term – Full Safety Population
15.2.6.5.1	Summary of Adverse Events by System Organ Class, Preferred Term and Relationship to Study Product Exposure and Expectedness – Safety Population
15.2.6.5.2	Summary of Adverse Events by System Organ Class, Preferred Term and Relationship to Study Product Exposure and Expectedness – Full Safety Population
15.2.6.6.1	Summary of Adverse Events by Product Use Category, System Organ Class, Preferred Term and Relationship to Study Product Exposure and Expectedness – Safety Population
15.2.6.6.2	Summary of Adverse Events by Product Use Category, System Organ Class, Preferred Term and Relationship to Study Product Exposure and Expectedness – Full Safety Population
15.2.6.7.1	Summary of Adverse Events Leading to Study Product Discontinuation, Interruption, or Reduction by System Organ Class and Preferred Term – Safety Population
15.2.6.7.2	Summary of Adverse Events Leading to Study Product Discontinuation, Interruption, or Reduction by System Organ Class and Preferred Term – Full Safety Population
15.2.6.8.1	Summary of Adverse Events Leading to Study Product Discontinuation, Interruption, or Reduction by Product Use Category, System Organ Class, and Preferred Term – Safety Population
15.2.6.8.2	Summary of Adverse Events Leading to Study Product Discontinuation, Interruption, or Reduction by Product Use Category, System Organ Class, and Preferred Term – Full Safety Population
15.2.6.9.1	Summary of Adverse Events Related to Study Procedure by System Organ Class and Preferred Term – Safety Population
15.2.6.9.2	Summary of Adverse Events Related to Study Procedure by System Organ Class and Preferred Term – Full Safety Population
15.2.6.10.1	Summary of Adverse Events by System Organ Class, Preferred Term and Severity – Safety Population
15.2.6.10.2	Summary of Adverse Events by System Organ Class, Preferred Term and Severity – Full Safety Population
15.2.6.11.1	Summary of Adverse Events by Product Use Category, System Organ Class, Preferred Term and Severity – Safety Population

TFL number	Title
15.2.6.11.2	Summary of Adverse Events by Product Use Category, System Organ Class, Preferred Term and Severity – Full Safety Population
LISTINGS	
15.3.6.1.1	Listing of Adverse Events

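### Ambulatory AEs are tabulated under one product-use category averaged over the whole 85 days, so product use after an AE can decide the column in which it is counted

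*SAP*

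**What the plan says.** Three SAP sections agree on the rule.

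- Section 12.6.4.2: "Ambulatory AE data will also be reported by product use category (see Table 20) defined on product use over the whole ambulatory period".
- Section 10.3.1: "Subjects in the safety populations will be analyzed according to product use categories defined over the whole ambulatory period".
- Section 12.1.5, on product use in safety summaries: the percentage of THS use is "calculated by averaging non missing consumption data over the entire ambulatory time interval".

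The percentage is THS sticks divided by THS sticks plus cigarettes (SAP 6.3.3.1). For AE tables the general scheme of SAP Table 20 applies to the THS arm: THS at 70% or more, Dual between 30% and 70%, CC at 30% or less. The by-category tables cover all AEs, relatedness, severity, AEs leading to study discontinuation, and Table 15.2.6.8, "Summary of Adverse Events Leading to Study Product Discontinuation, Interruption, or Reduction by Product Use Category".

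The protocol frames product use differently. Section 12.1.2 says that subjects with a THS pattern "over a defined period will be considered as THS 2.2 Menthol users during that period". Section 12.3 calculates dual use in successive windows, for example "on Day 60, using the reported number of cigarettes and/or Menthol Tobacco Sticks consumption after Day 30". Section 12.4.3 adds: "Subjects in the safety population will be analyzed according to actual exposure". Elsewhere the SAP also works by period. Section 12.1.1 says "Summaries of data by product use categories will be produced for the product use time periods 1 to 4", although it qualifies this as applying where appropriate.

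**The concern.** No rule links an AE to the product in use at or before its onset. Smoking cigarettes does not end participation in the ambulatory period, so a subject can use THS exclusively, have an AE, return to cigarettes and stay in the study. The later cigarettes then help decide where the earlier AE is counted. In Table 15.2.6.8 the event and the category are directly linked: stopping or reducing THS because of the AE, and then smoking, can itself move the subject out of the THS column.

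Both documents give the purpose of the coarser categories as understanding the product's impact on endpoints such as safety. A category fixed partly by what happened after the event serves that purpose poorly. It also fits poorly with the protocol's period-based, actual-exposure language, and SAP Section 9 does not list it as a change.

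**Working it through.** **Inputs.** The ambulatory period is 85 days (SAP 6.1; Day 91 − Day 6 = 85). The cut-offs are 70% and 30% (SAP Table 20). The documents give no figure for sticks per day relative to later cigarettes per day. That ratio, *r*, is an assumption: base case 1.0, range 0.75 to 1.5.

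**Formula.** For *d* days of exclusive THS followed by cigarettes only, share = 100 × *r* × *d* / (*r* × *d* + 85 − *d*).

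**Base case, *r* = 1.**

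| Days on THS | Share | Category |
|---|---|---|
| 25 | 25/85 = 29.4% | CC |
| 26 | 26/85 = 30.6% | Dual |
| 59 | 59/85 = 69.4% | Dual |
| 60 | 60/85 = 70.6% | THS |

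A complete change to cigarettes before about Day 66 (6 + 60) therefore takes the subject out of the THS category.

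**Sensitivity to *r*.** The CC limit is *d* = 0.3 × 85 / (0.3 + 0.7*r*), which runs from 30.9 days (*r* = 0.75) to 18.9 days (*r* = 1.5). The THS limit is *d* = 0.7 × 85 / (0.7 + 0.3*r*), which runs from 64.3 to 51.7 days. The limits move, but the effect remains.

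**Partial change after 24 exclusive days, *r* = 1.** The remaining 61 days are mixed use.
- Half and half: (24 + 0.5 × 61)/85 = 64.1%, Dual.
- 60% THS: (24 + 0.6 × 61)/85 = 71.3%, THS.

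**Opposite error, *r* = 1.** With 65 days of THS then 20 of cigarettes, 65/85 = 76.5%, so AEs during the cigarette days are counted under THS. With 25 days of cigarettes then 60 of THS, 60/85 = 70.6%, and early cigarette-period AEs are counted under THS.

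**Cases with no shift.** If a subject withdraws at the AE after 20 days of exclusive THS, only non-missing days are averaged: 20/20 = 100%, THS. If a subject stops THS and smokes no cigarettes, the denominator gains nothing and the share stays at 100%.

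**What period of onset would change.** Period 2 has about 30 − 6 = 24 days. For an AE on day 20, with cigarettes only after day 20, the whole-period share is 20/85 = 23.5% (CC), and the Period 2 share is 20/24 = 83.3% (THS). For an AE on day 10, with cigarettes only after day 10, the shares are 10/85 = 11.8% (CC) and 10/24 = 41.7% (Dual). Classifying by period reduces the problem but does not remove it, which is why Table 15.2.6.8 needs a pre-onset window.

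**The case against.** The case for leaving the plan alone has several good parts.

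- **The tables are supplementary.** The main AE tables are by study arm, with an ambulatory split. Table 15.2.6.7 gives the product-discontinuation events by arm, relatedness is tabulated, and all AEs are listed. None of these depends on the category. This stands.
- **The shift is conditional.** A reader might infer that every AE on exclusive THS, or every AE that stops THS use, ends up under Dual or CC. The SAP's formula does not support that. The overall share must fall below 70%, and subjects who withdraw or stop without smoking keep the THS category.
- **CC here is not the comparator.** A reader might infer that THS events are charged to the mCC arm. In Table 20, CC at 30% or less is a category within the THS arm, and the mCC arm has its own categories.
- **The net direction is not established.** A reader might infer that THS will look safer overall. Errors run both ways. Only for AEs that prompt a change to cigarettes is the direction clear.
- **The 50% figure does not measure this.** The plan expects half the THS arm to leave the ambulatory per-protocol set, but under a far stricter rule: more than 2 cigarettes on one day, or an average above 0.5 per day. Someone using 15 sticks and 1 cigarette daily fails that rule, yet has a share of 15/16 = 94% and stays in THS. The documents give no count of subjects affected.
- **The departure from the protocol is arguable.** The ambulatory period can be read as a defined period, actual exposure is not defined, and the SAP revision history records the choice openly. What remains is a poor fit with the protocol's windows and an omission from Section 9, not a concealed change.

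**Conclusion.** The mechanism is real and confined to the by-category AE tables. Use after an AE contributes to the category under which it is counted, so an AE during exclusive THS use can appear under Dual or CC, and an AE during cigarette use can appear under THS. At equal daily consumption with an abrupt, complete change, the boundaries are 25 and 60 days of 85. Over the assumed consumption ratios they are about 19 to 31 days and 52 to 64 days. These are illustrations of the rule. The documents support no estimate of how many subjects or events would move, and no claim about net bias across all AEs. Table 15.2.6.8 is most exposed, because its events can determine the category. The change is worth making because these are the tables meant to show AEs by product actually used, and the arm-level tables cannot do that.

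**What to change.** In SAP 10.3.1, 12.1.5 and 12.6.4.2, tabulate each ambulatory AE by the category of the period in which it starts (Periods 2, 3 and 4), with the subjects in that category in that period as the denominator. Derive the category from non-missing diary days, as the safety rule in 12.1.5 already does. The non-safety rule there replaces missing days with Baseline cigarette use when diary data are sparse, and could push THS users with diary gaps towards CC.

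For Table 15.2.6.8, classify events by consumption before onset within the period. Where the AE starts on the first day of a period, fall back to the preceding period (confinement, for Period 2). Report event and subject counts against the period-category denominators, with a footnote that events and denominators use different windows. Also reconcile the numbering: SAP 13.2 uses 15.2.6.8.1 and 15.2.6.8.2 for AEs leading to study discontinuation by actual exposure, which is not what 12.6.4.2.1 assigns to those numbers.

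If the whole-period tables are kept, label them supplementary, footnote that the category includes use after the AE, and list the departure from the protocol's period-based, actual-exposure definitions in Section 9.

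The cost is SAP wording and reprogramming from daily diary data and AE start dates that are already collected. A subject may appear in different columns in different periods, and outside Table 15.2.6.8 the onset-period category still includes some use after the AE.
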